6.2.1. Study Phases

6.2.1.1. Screening (Day -14 through -3)

Subjects can be pre-screened ahead of enrollment by telephone and invited to the research center. Upon arrival to the research center, the study procedures will be explained. All Subjects who sign the informed consent form and satisfy the inclusion/exclusion criteria will be enrolled into the study.

The initial Screening visit will be conducted between 14 and 3 days prior to Baseline/CRU Admission on Day 0. The following procedures/assessments will be performed at Screening:

1. Informed consent (must be done prior to **any** of the following procedures, including asking subjects to discontinue prohibited medications)
2. Eligibility review
3. Medical history and demographics
 - Date of birth
 - Sex
 - Race
 - Ethnicity
 - Height (in)
 - Weight (lbs)
 - BMI (calculated from height and weight)
 - Medical History (self-reported; include onset dates)
 - Heart Failure
 - Hypertension
 - Stroke
 - Myocardial infarction
 - Unstable angina
 - Atrial fibrillation/flutter
 - Presence of implanted ventricular assist device, cardiac defibrillator, CardioMEMS™ or pacemaker

- Chronic obstructive pulmonary disease
 - Diabetes mellitus
 - Hepatic/liver disease
 - Chronic Kidney disease (If yes, stage)
 - Stage 1: Normal kidney function (GFR >90 mL/min/1.73 m² with urine findings, structural abnormalities, or genetic traits)
 - Stage 2: Mildly reduced kidney function (GFR (60-89 mL/min/1.73 m²))
 - Stage 3a: Moderately reduced kidney function (GFR (45-59 mL/min/1.73 m²))
 - Stage 3b: Moderately reduced kidney function (GFR 30-44 mL/min/1.73 m²)
 - Stage 4: Severe reduced kidney function (GFR 15-29 mL/min/1.73 m²)
 - Stage 5: Kidney failure (GFR < 15 mL/min/1.73 m² or dialysis)
 - Depression
 - Hyperlipidemia
 - Obstructive sleep apnea
 - Current Smoker (not current smoker if stopped smoking for at least 12 months)
4. Complete/full physical examination as described in Section 6.2.2.1
 5. Temperature
 6. Blood pressure
 7. Heart rate
 8. Screening labs will be performed to measure sodium, potassium, calcium, chloride, magnesium, carbon dioxide, blood urea nitrogen, serum creatinine, glucose, hemoglobin, hematocrit and blood alcohol.
 9. Urine drug screen
 10. Serum pregnancy test (for females of child-bearing potential)
 11. 12-Lead ECG as described in 6.2.2.2
 12. Prior medication assessment

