4.4. HANDLING OF MISSING DATA

No plasma concentration estimates will be imputed for missing values. Missing values will be treated as if they were not scheduled for collection and only those

samples with reported concentration values will be included in the pharmacokinetic and statistical analysis.

Missing values for urine collections will not be imputed. Any subject with a missing value for any subinterval (e.g. 0-1 hour) involved in the 0-6, 0-8 or 0-12 results will be excluded from statistical analyses for the interval affected.

No imputation of missing data will be done for any other data. To handle missing or partial AE and concomitant medication dates, the following rules in 5.4.1 will be applied.

4.4.1. For Partial Start Dates:

1. If the year is unknown, then do not impute the date but assign a missing value.
2. If the month is unknown, then:
 - i. If the year matches the year of the first dose date, then impute the month of the dose date.
 - ii. Otherwise, assign "January."
3. If the day is unknown, then:
 - i. If the month and year match the month and year of the first dose date, then impute the day of the dose date.
 - ii. Otherwise, assign "01."

4.4.2. For Partial End Dates:

1. If the year is unknown, then do not impute the date but assign a missing value.
2. If the month is unknown, then assign "December."
3. If the day is unknown, then assign the last day of the month.

After implementing the rules above, to determine whether AEs (or medications) with missing start or stop dates are pre-treatment or on/after first or second treatment, the following strategy will be used:

1. If both start date and stop date are missing, then the most conservative approach is taken, and the AE (or medication) is classified as treatment emergent (or concomitant medication).
2. If the start date is missing but the stop date is not missing and is on or after the day of study dose administration for Period 1 or 2, then the most conservative approach is taken, and the AE (or medication) is treatment emergent (or concomitant medication).
3. If the start date is missing but the stop date is not missing and is before the day of study dose for Period 1 and after the date of signed informed consent, then the AE (or medication) is not a TEAE (or prior medication).

4. If the start date is not missing but the stop date is missing, then the most conservative approach is taken, and medication is concomitant while the AE is defined by start date.

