9.3.5.3. Prior and Concomitant Medications

This section details the approach for recording and analyzing all medications before and during the study. All medications will be coded using WHODrug GLOBALB3Mar23.

Prior Medications: Defined as medications taken before the screening visit and ended on the day before the first trial drug dose. All medications taken within 7 days of screening will be noted.

Concomitant Medications: Includes non-trial medications taken at any time during the trial, either continuing from before or starting after the first trial drug dose. Summaries and listings of all prior and concurrent medications will be provided for all subjects, detailed by treatment sequence, PT, and ATC 4th level. If a medication starts before study entry and continues through the study that will be considered both as prior and concomitant. Prior and concomitant medications will be summarized by treatment sequence and overall. All medications will be listed by treatment sequence and subject.

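### SAP 4.4.1 can impute a start date later than the recorded stop date, which leaves records that ended before dosing without a defined class

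*SAP*

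**What the plan says.** SAP 4.4.1 completes partial start dates for AEs and medications from the first dose date:

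- Day unknown (rule 3.i): "If the month and year match the month and year of the first dose date, then impute the day of the dose date". If month and year do not match, the day becomes the first of the month.
- Month unknown (rule 2.i): "If the year matches the year of the first dose date, then impute the month of the dose date". If the year does not match, the month becomes January.
- Year unknown (rule 1): "If the year is unknown, then do not impute the date but assign a missing value".

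SAP 4.4.2 completes partial end dates to the latest possible day. Four classification steps follow under the same heading, introduced by "After implementing the rules above, to determine whether AEs (or medications) with missing start or stop dates are pre-treatment". Steps 1 to 3 need a missing start, and step 4 needs a missing stop. Step 3 opens "If the start date is missing but the stop date is not missing and is before the day of study dose for Period 1". If the stop is also after consent, the item is a prior medication or not treatment-emergent.

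SAP 9.3.5.3 describes prior medications as "Defined as medications taken before the screening visit and ended on the day before the first trial drug dose". Concomitant medications are those taken during the trial, "either continuing from before or starting after the first trial drug dose".

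Under SAP 9.3.1 a Period 1 treatment-emergent AE must start at or after Period 1 dosing, and must have been absent beforehand or have worsened. An AE that cannot be classified defaults to treatment-emergent. AEs before Period 1 treatment are listed only.

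**The concern.** The start-date rules use only the first dose date. If the stop is already known to lie before dosing, moving the start to dosing day produces a record that begins after it ended. This is a stated rule giving a wrong date, not a missing detail.

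The order of operations removes the safeguard. Step 3 exists to keep items that ended before Period 1 dosing out of the on-treatment class, but imputation has already filled the start, so the step cannot act. The result is perverse. A record with no known start year is handled correctly, while a record for which the site knows the year, or the month and year, is not.

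At stake are the medication summaries and the TEAE tables. An AE misplaced in this way would be attributed to whichever treatment the subject received in Period 1.

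**Working it through.** The plan gives no figure to reproduce, so the check is to apply the rules in their written order to test records.

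**Inputs.** The rules are those of SAP 4.4.1, the four classification steps under 4.4.2, and SAP 9.3.5.3 and 9.3.1. The dates are assumed for illustration: first dose 15 June 2024, consent 5 June 2024.

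**Step 1: impute the start. Step 2: compare it with the stop. Step 3: look for a classification step that applies.**

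| Recorded start | Recorded stop | Imputed start | Start after stop? | Classification step |
|---|---|---|---|---|
| June 2024, day unknown | 14 June | 15 June | yes, by 1 day | none |
| June 2024, day unknown | 10 June | 15 June | yes, by 5 days | none |
| 2024, month and day unknown | 10 June | 15 June | yes, by 5 days | none |
| 2024, month and day unknown | 10 March | 15 June | yes, by 97 days | none |
| May 2024, day unknown | 10 June | 1 May | no | none needed for date order |
| June 2024, day unknown | 16 June | 15 June | no | none needed for date order |
| year unknown | 10 June | stays missing | not applicable | step 3: prior / not a TEAE |

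The 97 days are 21 (rest of March) + 30 + 31 + 15. In the two rows with month and day unknown, rule 2.i first supplies June and rule 3.i then supplies the 15th.

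First doses on 3 and 28 June give the same pattern. With dosing on 3 June and a stop on 2 June, the imputed start is 3 June. With dosing on 28 June and a stop on 27 June, it is 28 June. One test record is different: dosing on 3 June, start in June with day unknown, and stop on 29 May. There the recorded data already contradict each other, and no imputation rule can repair that.

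**Where the failing records go next.** Both dates are now filled, so they fall to the general definitions.

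- *Medication.* By its imputed start, the drug was not taken before screening, so it misses the prior definition. By its recorded stop, it was not continuing at dosing. A start on the dosing date is also not clearly after the dose. The SAP does not say which date governs, so the class is undefined.
- *AE.* The imputed start meets the date condition of the Period 1 definition. The second condition (absent beforehand, or worsened) should fail, because the event was present before dosing. A program that judges absence from the imputed start would not see that, and an AE treated as unclassifiable goes to treatment-emergent by default.

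**After the fix.** The start takes the earliest date its recorded parts allow: 1 June for June with day unknown, and 1 January 2024 for the year alone. In the four failing rows this is on or before the stop, and each record lies wholly before dosing.

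**The case against.** A reader might infer more than the documents support, in three ways.

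*That the SAP counts such a drug as concomitant.* It does not say so. SAP 9.3.5.3 also looks at when the drug ended, and a drug with a recorded stop before dosing is not continuing. Prior medications are also assessed separately at Screening and Baseline (Protocol 6.2.1.1 and 6.2.1.2). This objection stands: concomitant is only a possible programming outcome. It does not remove the gap, because the classification steps sort medications into prior and concomitant only after imputation.

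*That interacting drugs or diuretics would be reported as begun on dosing day, obscuring what was on board during sampling.* The consent wording in Protocol 6.2.1.1, "including asking subjects to discontinue prohibited medications", invites this. However, exclusion criterion 14 and Protocol 5.8 bar interacting drugs within 30 days, and Screening is at most 14 days before Day 0. Stopping such a drug in that window would therefore conflict with eligibility. The date and time of the last oral loop diuretic dose are recorded directly at Baseline and before Period 2. The summaries in SAP 9.3.5.3 are not described as showing start dates, and listings keep the recorded stop. This objection stands, and the point does not rest on those drugs.

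*That an AE resolved before dosing necessarily becomes treatment-emergent.* SAP 9.3.1 also requires absence before treatment or worsening, and sends AEs before Period 1 treatment to listings. Read in full, the definition should exclude such an AE. What remains is a risk, because the imputed start meets the date condition and unresolved cases default to treatment-emergent. Such AEs may also be few: Protocol 7.7.4 requires documentation of events after dosing, and the Screening and Baseline procedures list no AE assessment.

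**Conclusion.** The concern holds in a limited form. SAP 4.4.1 rules 2.i and 3.i give a start later than the stop for every record that meets two conditions: the known parts of the start match the first dose date, and the stop is before dosing. No classification step catches these records. A medication is left without a defined class, and an AE could be tabulated as treatment-emergent.

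The documents do not allow the number of such records to be estimated; it may be zero. For scale, with 21 subjects one misplaced AE in a subject with no other event in that category would move an incidence by 1/21 = 4.8 percentage points. In a period-specific table by treatment, assuming a 10/11 split of the 21, the shift would be 1/11 = 9.1 to 1/10 = 10.0 points.

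The AUC analyses use concentrations and sampling times, not these dates, so the primary conclusion is untouched. This is a minor correction, worth making because it is easy and the stated rule yields an impossible date.

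**What to change.** Make two additions to the SAP.

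1. In 4.4.1: an imputed start may not fall after the recorded or imputed stop date. If it would, use the earliest date consistent with the recorded part of the start (day 01, or 01 January). If even that date is after the stop, the recorded data conflict and the record should be queried, not imputed.
2. In the classification steps: any AE or medication with a recorded stop before the Period 1 dose is not treatment-emergent, or is a prior medication. This applies whether its start is complete, partial or missing, and whether the stop is before or after consent. A stop imputed under 4.4.2 can be treated the same way, since it is the latest date the record allows.

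Widening step 3 from missing to partial starts would not be enough. By then a partial start has become complete, and step 3 also requires a stop after consent.

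The cost is a few lines of SAP text and one programming check, with no effect on data collection or on the PK analysis.

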5. DEFINITIONS

Baseline Definition: Baseline for Period 1 is defined as Baseline Assessment (Day 0) (or Screening if missing) and for Period 2 as Pre-Period 2 Assessment (Day 3 ± 1).

Change from Baseline: The change from baseline values will be calculated as post-baseline value (p) minus the baseline value (b) for each Period 1 and 2.

Percent (%) Change from Baseline: The % change from baseline values will be calculated as $(p - b)/b \times 100$ for each Period 1 and 2.

6. ENDPOINTS

6.1. Pharmacokinetic Endpoints

For IV administration of furosemide injection, USP (reference), PK blood samples will be collected as follows:

- First IV 1 to 2-minute injection dose: Pre-dose and 5, 15, 30, 45 minutes and 1, 1.5, 2 hours after **start** of first IV dose. The sample taken at 2 hours will be drawn immediately prior to the start of the second IV dose.
- Second IV 1 to 2-minute injection dose (new clock for PK sampling starts upon the start of administration of second IV dose): 5, 15, 30, 45 minutes and 1, 1.5, 2, 3, 4, 6, 8 and 10 hours after **start** of second IV dose.

For the SC administration of SCP-111 (test), PK blood samples will be collected as follows:

- Pre-dose and 5, 15, 30, 45 minutes and 1, 1.25, 1.5, 2, 3, 4, 5, 6, 8 and 12 hours after the SC injection

Individual pharmacokinetic parameters for furosemide will be summarized with descriptive statistics. Pharmacokinetic parameters including:

- the maximum observed plasma concentration (C_{max}),
- the area under the plasma concentration versus time curve from time 0 (pre-dose) to the last quantifiable time point (AUC_{last}),
- the AUC from time 0 (pre-dose) to time infinity (AUC_{inf}),
- the time to C_{max} (T_{max}), the terminal phase elimination rate constant (λ_z), the terminal elimination half-life ($t_{1/2}$) for both SC SCP-111 (test) and IV furosemide (reference),

- the apparent systemic clearance (CL/F) for SC SCP-111 and systemic clearance (CL) for IV furosemide,
- the apparent systemic volume of distribution (Vz/F) for SC SCP-111

Systemic volume of distribution (V) for IV furosemide will be calculated using non-compartmental analysis.

Bioavailability of SC SCP-111 will be determined based on the geometric mean ratios of AUC_{last} and AUC_{inf} of IV furosemide (reference) and SC SCP-111 (test) and 90% confidence intervals on these ratios.

Geometric mean ratios of C_{max} of IV furosemide (reference) and SC SCP-111 (test) and 90% confidence intervals on these ratios will also be determined.

6.2. Pharmacodynamic Endpoints

Urine will be collected from spontaneous voids in 1-hour increments for the first 8 hours and in 2-hour increments up to 12 hours post-dose. Total urine output, urinary sodium, and potassium excretion for each collection interval ((0-1), (1-2), (2-3), (3-4), (4-5), (5-6), (6-7), (7-8), (8-10) and (10-12) hours after initiation of dosing) will be recorded.

The following PD parameters will be evaluated for IV furosemide and SC SCP-111 subcutaneous administration:

Urine Output:

- Measured at 0-6 hours, 0-8 hours, and 0-12 hours
- The sum of urine output for intervals 0-1, 1-2, 2-3, 3-4, 4-5 and 5-6 comprise 0–6-hour urine output.
- The sum of urine output for intervals 0-1, 1-2, 2-3, 3-4, 4-5, 5-6, 6-7 and 7-8 comprise 0–8-hour urine output.
- The sum of urine output for intervals 0-1, 1-2, 2-3, 3-4, 4-5, 5-6, 6-7, 7-8, 8-10 and 10-12 comprise 0–12-hour urine output.

Urinary Sodium Excretion:

- Measured at 0-6 hours, 0-8 hours, and 0-12 hours
- Calculated as: Urinary Sodium Excretion=Total Urine Output (L) × Sodium Concentration (mEq/L)

Urinary Potassium Excretion:

- Measured at 0-6 hours, 0-8 hours, and 0-12 hours
- Calculated as: Urinary Potassium Excretion=Total Urine Output (L) × Potassium Concentration (mEq/L)

Example Calculation:

- **Interval: 0-1 hour**

Total Urine Output=0.5 L

Sodium Concentration=100 mEq/L

Urinary Sodium Excretion=0.5 L×100 mEq/L=50 mEq

- **Interval: 1-2 hours**

Total Urine Output=0.4 L

Sodium Concentration=90 mEq/L

Urinary Sodium Excretion=0.4 L×90 mEq/L=36 mEq

Continue this calculation for each subsequent interval (e.g., 0-1, 1-2, 2-3, 3-4, 4-5, 5-6, 6-7, 7-8, 8-10, and 10-12 hours) to obtain the total urinary sodium excretion for each time period.

Same calculations are conducted to calculate urinary potassium excretion for each interval.

The sum of intervals 0-1, 1-2, 2-3, 3-4, 4-5 and 5-6 comprise 0-6 hour urinary sodium/potassium excretion.

The sum of intervals 0-1, 1-2, 2-3, 3-4, 4-5, 5-6, 6-7 and 7-8 comprise 0-8 hour urinary sodium/potassium excretion.

The sum of intervals 0-1, 1-2, 2-3, 3-4, 4-5, 5-6, 6-7, 7-8, 8-10 and 10-12 comprise 0-12 hour urinary sodium/potassium excretion.

6.3. Safety and tolerability

Adverse Events (AEs) and Serious Adverse Events (SAEs) will be grouped by body system and summarized. The incidence (number and percentage of subjects) of adverse events and serious adverse events will be presented overall and by MedDRA System Organ Class (SOC) and Preferred Term (PT).

6.4. Injection Site Pain

Injection site pain will be assessed using an 11-point scale where 0 is equivalent to no pain and 10 is equivalent to the worst possible pain. For IV administration, the 11-point pain scale will be performed pre-dose, after IV needle placement, immediately after 1st dose, and 15 and 30 minutes after 1st dose, immediately after 2nd dose, and 15 and 30 minutes and 4 and 10 hours after the 2nd dose. For SC administration, the 11-point pain scale will be performed pre-dose, immediately after dose and 15 and 30 minutes and 6 and 12 hours after dose. Pain requiring treatment, withdrawal from the study or discontinuation of study drug will also be recorded as an adverse event (AE).

7. INTERIM ANALYSIS

There will be no formal interim analysis.

8. ANALYSIS POPULATIONS

The statistical analyses and summaries will be based on the study populations detailed below.

The subject demographics, baseline characteristics and the other endpoints will be based on the Full Analysis Set (FAS) population. The PK Analysis will be performed on the Bioavailability (BA) population.

- **Full Analysis Set (FAS) Population:** This includes all participants who were randomized in the study, regardless of whether they completed the study as per protocol.
- **Pharmacokinetic (PK) Population** will include all randomized subjects who receive full 80 mg dose of furosemide study drug AND have sufficient samples collected for estimation of pharmacokinetic parameters.
- **Bioavailability (BA) Population** will include all subjects in the PK population who have a sufficient number of samples collected for estimation of pharmacokinetic parameters after receiving BOTH IV furosemide and SC SCP-111.

All Safety analyses will be based on the safety population.

- **Safety Population** will include all randomized subjects who received at least 1 dose of either study drug and have provided at least 1 post-baseline safety assessment.

9. STATISTICAL ANALYSIS

This is an open-label, single-dose, randomized, two-way (two-period) crossover Study to Compare the Pharmacokinetics and Pharmacodynamics of SCP-111 (furosemide injection). The SAP takes precedence over the protocol.

9.1. Pharmacokinetic Analyses

The analyses will be performed on subjects in the Bioavailability Population.

Derived plasma PK parameters will be tabulated and summarized by treatment. Descriptive statistics for PK parameters (C_{max} , T_{max} , AUC_{last} , AUC_{inf} , AUC_{ext} , λ_z , $t_{1/2}$, V , V_z/F , CL , CL/F , and F) will include the arithmetic mean, CV%, SD of the arithmetic mean, median, minimum, maximum, and N. The geometric mean and geometric CV% will be estimated for C_{max} , AUC_{last} , and AUC_{inf} , only.

Statistical analyses will be performed using the General Linear Models (GLM) procedure of the SAS statistical program (PC version 9.4). The naturally log-transformed (ln-transformed) pharmacokinetic parameter estimates (for C_{max} , AUC_{last} , and AUC_{inf} , only), as well as the concentrations at each scheduled sample time will be evaluated by analysis of variance.

The statistical model will contain the main effects of sequence, subject nested within sequence, treatment and period. F-ratios for testing main effects will be constructed using the mean square term for the effect as the numerator and the mean square error term from the ANOVA as the denominator. The F-ratio to test for sequence effects will be constructed using the type III mean square term for sequence as the numerator and type III mean square for subjects nested within sequence as the denominator. Hypothesis testing will be conducted at $\alpha = 0.05$, except in the case of sequence effects which uses $\alpha = 0.10$.

The PK Analysis report will discuss any statistically significant effect found for AUC or C_{max} .

The intra-subject coefficient of variation will be estimated from the mean square error term (MSE) of the ln-transformed (loge) results as:

$$100\% * \text{SQRT}(e^{\text{MSE}} - 1)$$

Confidence Intervals (90%) for the area under the curve (AUC) and peak concentration (C_{max}) comparisons are to be calculated by the t-test approach (2,1 sided) at $\alpha = 0.10$ overall, $\alpha = 0.05$ each side:

$$\text{Interval Lower Limit} = (X_{SC} - X_{IV}) - Se * t_{\alpha/2}$$

$$\text{Interval Upper Limit} = (X_{SC} - X_{IV}) + Se * t_{\alpha/2}$$

Where X_{SC} , X_{IV} are the SC SCP-111 and IV furosemide treatment least-squares means, respectively.

SE is the standard error of the estimated difference between means from the SAS estimate statement.

$t_{\alpha/2}$ is the critical value from the t-distribution with degrees of freedom that of the error term and $\alpha = 0.10$.

For ln-transformed data, the interval will be calculated from the ANOVA results on the transformed values and then exponentiated to convert to the non-transformed scale:

$$\text{Interval Limit} = e(\ln\text{-transformed interval limit})$$

The intervals will be computed for the "true" mean treatment differences and true geometric mean ratios (from logarithmic transformation).

Similarly, the exponentiated difference between the SC SCP-111 and IV furosemide least squares means from ln-transformed results provided an estimate of the geometric mean test-to-reference ratio.

If there are multiple dosing groups, and subjects within each group receive their first and second doses on the same dates, adjustments to the statistical model for PK parameter analyses will be made.

